There are no other drugs approved for reduction of VOCs in children with SCD with a similar mechanism of action as ticagrelor. Hydroxyurea is approved for use in children with SCD in some markets and more recently, L-glutamine was approved by the US FDA. Evaluation of ticagrelor when given in addition to standard of care including these medications, where available and when considered medically appropriate, is considered acceptable for studying the efficacy and safety of ticagrelor in this patient group as compared with placebo.

Treatment duration is at least 12 months for study participants, but no longer than 24 months for any patients. The expected average follow-up is 18 months, assuming a uniformly distributed enrolment period of 12 months. Considering inclusion of patients with at least 2 VOCs in the past year, this treatment duration is considered long enough to evaluate effects on VOC events as well as to capture safety and tolerability data supporting a potential future long-term use of ticagrelor.

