8.2 Sample size estimate

The number of VOCs is assumed to have a negative binomial distribution with shape parameter 0.8. The mean number of crises per year is assumed to be 2.0 in the placebo group with reduction of 50% in the ticagrelor group. Patients will be randomised to 1:1 ratio and with minimum follow-up of 12 months and average follow-up of 18 months, 154 patients provide about 90% power for a 2-sided test of the mean number of crises for ticagrelor versus placebo, at significance level 5%. Allowing for dropouts, the sample size is increased to 182. The calculations were based on simulation with 5,000 repetitions.

Scenarios and simulations were evaluated to assess the risk with shorter and longer mean follow-up time. To ensure that the study is adequately powered the recruitment rate will be monitored and the sample size may be adjusted to a maximum of 200 patients. With a mean follow-up time of 13 month, 200 patients will provide 90% power to detect a reduction of 50% in the ticagrelor group.

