1.3 Number of Patients

The sample size was derived under the assumptions that the number of VOCs has a negative binomial distribution with shape parameter 0.8 and that the mean number of crises per year is 2.0 in the placebo group with reduction of 50% in the ticagrelor group. Considering that patients will be randomised in a 1:1 ratio, with minimum follow-up of 12 months and average follow-up of 18 months, 154 patients will provide about 90% power for a 2-sided test of the mean number of crises for ticagrelor versus placebo, at significance level 5%. Allowing for dropouts, the sample size is increased to 182. The calculations were based on simulation with 5,000 repetitions. Scenarios and simulations were evaluated to assess the risk with shorter and longer mean follow-up time. To ensure that the study is adequately powered the recruitment rate will be monitored and the sample size may be adjusted to a maximum of 200 patients. With a mean follow-up time of 13 months, 200 patients will provide 90% power to detect a reduction of 50% in the ticagrelor group.

The randomisation codes will be computer-generated by Parexel Informatics and loaded into the Interactive Voice/Web Response System (IxRS) database. Randomisation codes will be generated in blocks to ensure approximate balance (1:1) between the two randomised treatment groups (ticagrelor or placebo twice daily [bd]). Stratification for baseline hydroxyurea use (Yes/No) by country will be applied.

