 - (b) Treatment group, baseline hydroxyurea use (Yes/No), prior VOC events in previous 12 months prior to study enrolment at screening (Visit 1) (\geq 2 to \leq 4, > 4), as collected on the VOC eCRF
 - (c) Treatment group, baseline hydroxyurea use (Yes/No), and geographic region
 - (d) Where geographic region is defined as:
 - North and South America (USA, Canada, Brazil)
 - Europe (UK, Turkey, Spain, Italy, Greece, Belgium)
 - Africa and Asia (Egypt, Ghana, India, Kenya, Lebanon, South Africa, Tanzania, Uganda)

- (e) Treatment group, baseline hydroxyurea use (Yes/No), age group at randomisation (Visit 2) (≥ 2 years to < 12 years, ≥ 12 years to < 18 years), prior VOC events in previous 12 months prior to study enrolment at screening (Visit 1) (≥ 2 to ≤ 4 , > 4), as collected on the VOC eCRF, and geographic region
- 6 Zero-inflated Poisson and zero-inflated negative binomial models will be run on the same data as used for the primary analysis to allow for over dispersion seen in the negative binomial and Poisson models. The models allow for the excessive zero counts in the data. The zero-inflated Poisson and negative binomial models split the data into two separate distributions where one distribution (either Poisson or negative binomial) that generate both zero and non-zero counts, the second distribution is a constant distribution that generates only zero counts. When a zero count is observed, there is some probability, called the zero-inflation probability, that the observation came from the always-zero distribution; the probability that the zero came from the Poisson/negative binomial distribution is 1 minus the zero-inflation probability. When the underlying count distribution is a Poisson distribution, the mixture is called a zero-inflated Poisson (ZIP) distribution; when the underlying count distribution is a negative binomial distribution, the mixture is called a zero-inflated negative binomial (ZINB) distribution (Hilbe 2007).

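### The zero-inflated Poisson sensitivity analysis, with ordinary model-based standard errors, gives an interval about half the proper width under the plan's own negative binomial assumption

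*SAP*

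**What the plan says.** SAP 4.2.6.3 lists, among the sensitivity analyses that will be performed, item 6: "Zero-inflated Poisson and zero-inflated negative binomial models will be run on the same data as used for the primary analysis". The reason given is that these models accommodate overdispersion and an excess of zero counts. The item has no condition attached. It does not state the variance estimator, the covariates of the zero part, the offset, which ratio will be reported, or how to choose between the two models.

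The planning model is different. Protocol 8.2 states: "The number of VOCs is assumed to have a negative binomial distribution with shape parameter 0.8". SAP 1.3 repeats it: "the number of VOCs has a negative binomial distribution with shape parameter 0.8". Neither mentions a class of patients who cannot have a VOC. The primary analysis (SAP 4.2.6.1) is a negative binomial rate ratio with treatment, baseline hydroxyurea use and a log follow-up offset. SAP 4.2.6.2 tests the negative binomial against the Poisson, but no matching comparison of ZIP with ZINB is planned.

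**The concern.** ZIP has one way to produce extra variance: an always-zero class. Patients outside that class are treated as Poisson with a common rate given the covariates. The plan instead assumes strong variation in rate between all patients. Data of that kind contain many zeros, which ZIP absorbs, and a long upper tail, which it cannot. Its likelihood then treats the high counts as much more informative than they are, and the model-based standard error comes out too small.

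A sensitivity analysis is read for whether it agrees with the primary result. One whose interval is far too narrow can appear to confirm a borderline primary result. It can also contradict a null one and then have to be explained away after unblinding.

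**Working it through.** **Inputs.** Protocol 8.2 gives the rates: "The mean number of crises per year is assumed to be 2.0 in the placebo group with reduction of 50% in the ticagrelor group". The same section sets equal allocation, at least 12 and on average 18 months of follow-up, and 154 patients for about 90% power at two-sided 5%; dropout raises the number to 182. Protocol 1.2.2: "The expected average follow-up is 18 months, assuming a uniformly distributed enrolment period of 12 months", so follow-up t is taken as uniform on 1 to 2 years. Hydroxyurea prevalence is not given; 50% with no effect on the rate was assumed. The primary offset was carried over to ZIP.

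**1. Which variance does shape 0.8 mean?** Var(log RR) = Σ over arms of 1/[n·E{μ/(1+kμ)}]. Take k = 1/0.8 = 1.25 and n = 77 per arm.
- Placebo, μ = 2t: E = 0.8[1 − 0.4·ln(6/3.5)] = 0.6275.
- Ticagrelor, μ = t: E = 0.8[1 − 0.8·ln(3.5/2.25)] = 0.5172.
- Variance = 1/(77×0.6275) + 1/(77×0.5172) = 0.0207 + 0.0251 = 0.0458; SE = 0.214.
- Power = Φ(0.693/0.214 − 1.96) = Φ(1.28), about 90% (simulated 89.7%).

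The plan's figure reproduces. With k = 0.8 the power would be 96.4%, which does not. The plan therefore means variance = μ + 1.25μ².

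**2. Why ZIP fails on such data.** Take placebo at 1.5 years, μ = 3. The planned variance is 3 + 1.25×9 = 14.25. Fitted to no-effect data, ZIP puts about 27.5% of patients in an always-zero class, though none exists. The remaining 72.5% have mean 3/0.725 = 4.14, and ZIP takes their variance to be 4.14 too. Their actual variance is (14.25 + 9)/0.725 − 4.14² ≈ 14.9. The implied ratio of model SE to true SD is √(4.14/14.9) ≈ 0.53.

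**3. Simulation under no effect.** 1,500 trials per row; ZIP by maximum likelihood, constant zero part, model-based SE. NB is the primary model.

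| Setting | N | Mean SE | True SD | Ratio | ZIP rejects | ZIP, sandwich SE | NB rejects |
|---|---|---|---|---|---|---|---|
| 2.0/year, 12–24 months | 154 | 0.098 | 0.195 | 0.50 | 33.0% | 6.1% | 5.1% |
| Same | 182 | 0.090 | 0.175 | 0.51 | 31.7% | 5.5% | 5.1% |
| Variance μ + 0.8μ² | 182 | 0.090 | 0.156 | 0.58 | 26.5% | 5.4% | 5.3% |
| Follow-up 0.25–1.5 years (assumed) | 182 | 0.123 | 0.203 | 0.61 | 22.0% | 6.5% | 5.0% |
| 1.0/year in both arms | 182 | 0.136 | 0.200 | 0.68 | 18.1% | 5.7% | 5.1% |

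Monte Carlo error is about 1.2 points for the ZIP column. Repeat runs at the planned rate and follow-up gave 29–33%, and 24% with the shorter follow-up. The rejection rate follows from the ratio: 2Φ(−1.96×0.51) = 2Φ(−1.00) = 31.7%. Putting treatment in the zero part hardly changes the results (31.7% in row 2). ZINB rejects 5.3% in row 2 (likelihood ratio test).

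The table also bounds the disagreement with the primary test. In row 2, ZIP is significant and the primary test is not in at least 31.7 − 5.1 = 26.6% of trials. In the last row the bound is 18.1 − 5.1 = 13.0%.

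**4. Simulation at the planned effect (true ratio 0.50, N = 154).**
- Estimated ratios: negative binomial 0.501; ZINB 0.501; ZIP 0.556 with a constant zero part; ZIP count part 0.573 with treatment in the zero part.
- ZIP with a constant zero part has SE 0.129 against a true SD of 0.214. The bias is ln(0.556/0.50) = 0.106 and the half-width is 1.96×0.129 = 0.253. Approximate coverage of 0.50 is Φ(0.147/0.214) − Φ(−0.359/0.214) = 0.754 − 0.047 = 71%. Coverage counted in simulations was 68% and about 70%.

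**5. Which quantity ZIP estimates.** The overall mean ratio is (1−π_T)λ_T / [(1−π_P)λ_P], where π is the zero-inflation probability and λ the count-part mean. If π is constant it cancels and leaves λ_T/λ_P, the count-part ratio. If treatment enters the zero part it does not cancel; computing the overall ratio from that fit gives 0.502.

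**The case against.** Four points can be made for the SAP.

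First, it does not say that standard errors will be model-based, and sandwich errors bring rejection back to about 5–6%. That is right, and every figure above for the error bars rests on this assumption. But model-based errors are the ordinary output of a maximum-likelihood fit, and nothing in item 6 asks for anything else.

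Second, a reader might infer that ZIP can make an ineffective drug succeed. The documents do not support that. SAP 4.1.1 attaches the 5% level to the primary endpoint, SAP 4.2.6.1 fixes the negative binomial model for it, and item 6 has no decision rule. ZINB is required on the same data and behaves correctly, so a narrow ZIP interval would stand beside two sound ones.

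Third, a reader might infer that the ZIP ratio is always a different quantity from the primary rate ratio. That holds only if treatment enters the zero part, which the SAP does not state. With a constant zero part the ratio is formally the overall one. The shift from 0.50 to 0.56 is then misspecification bias towards no effect, and reporting an overall ratio would not remove it. Under no effect both ratios equal 1.

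Fourth, this SAP edition was revised for early termination (SAP 3.1.4.1), so the 12-month minimum follow-up is no longer assured. The half-size error and the 30% belong to the planned design. The milder settings still reject at more than three times the nominal rate.

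**Conclusion.** The point stands in limited form: wrong as written, as regards the error bars. ZIP does not deliver the protection against overdispersion for which item 6 includes it. Under the plan's assumptions, with model-based standard errors, its SE is about half the true SD and it rejects about 30% of the time under no effect. With an assumed shorter follow-up or a rate of 1.0/year the rejection rate is about 18–25%. At a true ratio of 0.50 it is biased towards no effect (about 0.56), and its interval covers the truth in about 70% of trials or slightly fewer.

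The primary result and its type I error are untouched, and ZINB in the same item is sound. The cost is false reassurance, or a spurious conflict, when the ZIP row is read as a robustness check. The figures assume negative binomial counts with no structural zeros, follow-up as stated in each setting, and no hydroxyurea effect.

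**What to change.** In SAP 4.2.6.3, item 6:
- Keep ZINB.
- Either drop ZIP, or report it only with empirical (sandwich) standard errors. Dropping it is cleaner: the sandwich repairs the interval width but not the bias. At the planned effect with N = 154, ZIP with sandwich errors rejects in 78.9% of trials against 89.7% for the primary model.
- State the offset and the zero-part covariates for each model retained.
- If treatment is in the zero part, report the ratio between arms of (1 − zero-inflation probability) × mean, with a delta-method or bootstrap 95% interval, so that it matches the primary rate ratio.

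The cost is a few lines of SAP text and program code, with one table fewer if ZIP is dropped. No new data are needed.

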4.2.6.4 Subgroup analyses

To explore the uniformity of the detected overall treatment effect on the primary efficacy variable, subgroup analyses and statistical modelling including testing for interaction between treatment and covariates will be performed on the full analysis set for the factors below.

If there are issues with model convergence, only descriptive statistics by subgroup will be presented. Descriptive statistics by subgroup will be presented for all cases regardless of the model convergence. These analyses are exploratory and the results from these analyses will not affect the choice of terms used in the model for the primary analysis.

The following subgroups will be reported:

- Age by category:
 - ≥ 2 years to < 12 years at randomisation (Visit 2)
 - ≥ 12 years to < 18 years at randomisation (Visit 2)
- Number of VOC events within the previous 12 months prior to study enrolment at screening (Visit 1):
 - ≥ 2 to ≤ 4
 - > 4
- Baseline hydroxyurea use: Based on IxRS
 - Yes
 - No

- Sickle cell genotype: HbSS and HbSB⁰ Thalassaemia
- Geographic region:
 - North and South America (USA, Canada, Brazil)
 - Europe (UK, Turkey, Spain, Italy, Greece, Belgium)
 - Africa and Asia (Egypt, Ghana, India, Kenya, Lebanon, South Africa, Tanzania, Uganda)
- Gender: Male and Female
- Race as reported in [Appendix B Race Mapping](#):
 - White
 - Black or African-American
 - Asian
 - Other

If the negative binomial regression model is judged to be appropriate, then for each subgroup analysis separately, where sufficient data allows, a negative binomial regression model will be fitted including as covariates treatment group, subgroup main effect and the treatment-by-subgroup interaction. The p-value for the treatment-by-subgroup interaction will be presented.

The logarithm of the patient's observed follow-up time per defined treatment period expressed in years (where a year = 360 days) will be used as an offset term in the model to adjust for patients having different follow-up times.

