3.5 Methods for assigning treatment groups

The randomisation codes will be computer generated by AstraZeneca R&D and loaded into the IXRS database. Randomisation codes will be generated in blocks to ensure approximate balance (1:1) between the 2 treatment arms (ticagrelor or placebo bd). Stratification for baseline hydroxyurea use by country will be applied.

For each patient randomised the IXRS will provide the Investigator with a unique kit ID number matching the treatment arm assigned to the patient. Following randomisation, the first dose of study drug will be administered to the patient as soon as possible. At randomisation and subsequent dispensing visits, the patient should always be provided medication with the kit ID(s) allocated by the IXRS. If a patient receives the incorrect randomised treatment at any time during the study, this must be corrected as soon as discovered after discussing with the Study Physician.

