4.2.6 Primary Efficacy Variable

4.2.6.1 Number of VOCs

The primary efficacy variable is the number of VOC events during the defined treatment period (refer to Section 3.1.4) and the primary analysis is to compare the VOC event rate of ticagrelor with placebo based on the intent to treat (ITT) principle. The primary efficacy analysis will be performed using FAS (refer to Section 2.1).

The null hypothesis is that the VOC event rate on ticagrelor is equal to the VOC event rate on placebo. The alternative hypothesis is that the VOC event rate on ticagrelor is not equal to the VOC event rate on the placebo, ie,

H_0 : Rate ratio (ticagrelor vs placebo) = 1

H_a : Rate ratio (ticagrelor vs placebo) \neq 1

The VOC event rate on ticagrelor will be compared to the VOC event rate on placebo using a negative binomial model for the primary analysis. The response variable in the model will be the number of VOC events experienced by a patient during the defined treatment period, regardless of premature discontinuation of study treatment. The model will include covariates of treatment group and baseline hydroxyurea use (Yes/No) as covariates.

The logarithm of the patient's observed follow-up time per defined treatment period expressed in years (where a year = 360 days) will be used as an offset term in the model to adjust for patients having different follow-up times.

The estimated treatment effect (ie, the rate ratio of ticagrelor versus placebo), the corresponding Wald 95% confidence interval (CI) and the p-value for the rate ratio will be presented. In addition, the VOC event rate and the corresponding 95% CI within each treatment group will be presented. The VOC event rate will be computed using the OM option in the LSMEANS statement of PROC GENMOD.

An estimated value of the rate ratio < 1 will favour ticagrelor. The estimated dispersion parameter will also be noted.

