4.2.6.2 Testing the Fit of Negative Binomial Distribution

The fit of the negative binomial distribution to the data will be tested by means of the Pearson goodness of fit test after estimating the parameters of the distribution and checking whether there are no convergence issues with the maximum likelihood estimation of the coefficients. The negative binomial model will be tested against the Poisson model in a likelihood ratio test to test the robustness of the model.

If the negative binomial distribution is not appropriate, a stratified Wilcoxon rank sum test will be used. As the stratified Wilcoxon rank sum test cannot be adjusted for the patient's follow-up time, the annualised number of VOC events will be used for the analysis rather than the number of VOCs as analysed for the primary efficacy. . By using annualised number of VOC events, it scales it allowing a comparison of VOC rates across patients with varying time in the study. Baseline hydroxyurea use (Yes/No) will be used as a stratification factor. Number of annualised VOC events is the count of VOC events experienced by a patient over the defined treatment period (refer to Section 3.1.5) as assessed by the investigator and collected on the VOC1 eCRF, multiplied by 360 days, and divided by the number of days in the defined treatment period.

$$\text{Num VOCs Annualised} = \frac{\text{Number of VOCs}}{(\text{defined treatment period end date} - \text{randomisation date}) + 1} * 360$$

A Wilcoxon rank sum test for each subgroup defined in Section 4.2.6.4 will also be presented. No stratification factor will be included in this analysis.

Median, median difference and 95% confidence interval for the median difference will be estimated using Hodges-Lehmann method. Summary statistics of the annualised VOC rate will also be presented.

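### Six of the seven exploratory subgroup models in SAP 4.2.6.4 leave out baseline hydroxyurea, at a small cost in precision and in protection against chance imbalance

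*SAP*

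**What the plan says.** SAP 4.2.6.4 names seven subgroup factors: age, prior VOC events, baseline hydroxyurea, genotype, region, gender and race. For each factor separately, "a negative binomial regression model will be fitted including as covariates treatment group, subgroup main effect and the treatment-by-subgroup interaction", with log follow-up time as the offset. One factor is hydroxyurea itself ("Baseline hydroxyurea use: Based on IxRS"), so that model contains it as the subgroup main effect. The other six do not.

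Elsewhere hydroxyurea is kept:

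- Primary model, SAP 4.2.6.1: "The model will include covariates of treatment group and baseline hydroxyurea use (Yes/No) as covariates".
- Sensitivity analysis 5, SAP 4.2.6.3, keeps it beside age, prior VOC events and region, for example "Treatment group, baseline hydroxyurea use (Yes/No), and geographic region".
- Fallback overall Wilcoxon test, SAP 4.2.6.2: stratified by hydroxyurea. For the subgroup version the same section says "No stratification factor will be included in this analysis".
- Randomisation, Protocol 3.5: "Stratification for baseline hydroxyurea use by country will be applied". SAP 1.3 agrees.

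On the status of the subgroup results, SAP 4.2.6.4 says "These analyses are exploratory and the results from these analyses will not affect the choice of terms used" in the primary model.

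**The concern.** The stated purpose of the subgroup section is to see whether the overall treatment effect is uniform. That is easiest to read when the subgroup estimates come from the model that produced the overall effect, extended by the subgroup terms. Here age, prior VOC events and region are analysed with hydroxyurea in 4.2.6.3 and without it in 4.2.6.4, and no reason is given.

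Hydroxyurea is a plausible predictor of the outcome. Protocol 1.1 says that it lowers the rate of painful crises and ACS, and that it is not approved for children in all markets, so use probably varies by region. Leaving out a prognostic covariate has two costs. The unexplained variation between patients grows, which widens the interaction estimate. In addition, any chance difference between arms in hydroxyurea use within a subgroup goes uncorrected. Randomisation did not stratify on age, prior VOC events, genotype, gender or race, so such differences can arise there.

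**Working it through.** **1. Inputs.** From Protocol 8.2: negative binomial counts with shape 0.8 (dispersion k = 1/0.8 = 1.25), placebo rate 2.0 per year, 50% reduction, 1:1 allocation, mean follow-up 1.5 years, 154 evaluable of 182 patients. Assumed, because the documents are silent: hydroxyurea prevalence, its rate ratio, a 50/50 subgroup split, and follow-up uniform over 12 to 24 months.

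**2. The plan's own figure.** With 77 patients per arm, the variance of the log rate ratio is [1/(2.0 × 1.5) + 1/(1.0 × 1.5) + 2 × 1.25]/77 = 3.5/77 = 0.0455, so SE = 0.213. Power = Φ(0.693/0.213 − 1.96) = 90.2%. Simulation of 5,000 trials gives 90.4%. The stated 90% is reproduced, which confirms that 0.8 is the gamma shape.

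**3. Interaction, hydroxyurea irrelevant.** Four cells of 38.5 patients give variance 2 × 3.5/38.5 = 0.182, so SE = 0.426.

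**4. Does omission bias the treatment ratio?** Take 50% use and a hydroxyurea rate ratio of 0.5, the same in both arms. Placebo rates of 2.667 and 1.333 average 2.0; ticagrelor rates of 1.333 and 0.667 average 1.0. The ratio is 0.5 within each hydroxyurea level and also overall. With a log link and balanced arms, omission does not move the ratio unless hydroxyurea modifies the effect of ticagrelor.

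**5. Interaction SE with hydroxyurea omitted versus included.** 154 patients, prevalence 30, 50 and 70%, 1,500 simulated trials per scenario:

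| Assumed hydroxyurea rate ratio | Ratio of model SEs | Ratio of empirical SEs |
|---|---|---|
| 1.0 | 1.00 | 0.99–1.00 |
| 0.8 | 1.00 | 0.99–1.00 |
| 0.6 | 1.01–1.02 | 1.01–1.04 |
| 0.5 | 1.02–1.03 | 1.03–1.05 |

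At 0.5 and 50% use the SEs are 0.444 and 0.431. Mean interaction ratios lie between 0.98 and 1.01 under both models (true value 1). With use of 20% versus 80% in the two subgroups, the ratio of model SEs is 1.00–1.02, again without bias.

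**6. Use differing between subgroups, stronger effect.** 182 patients, 60% versus 40% use, 2,000 trials per scenario:

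| Rate ratio | Model SE omitted / included | Ratio | Empirical ratio | Mean interaction ratio, omitted / included | SD of within-trial difference in log interaction |
|---|---|---|---|---|---|
| 0.6 | 0.403 / 0.397 | 1.016 | 1.02 | 1.00 / 0.99 | 0.11 |
| 0.5 | 0.411 / 0.399 | 1.029 | 1.06 | 0.98 / 0.98 | 0.14 |
| 0.43 | 0.417 / 0.400 | 1.042 | 1.06 | 1.00 / 1.00 | 0.17 |

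A separate run at 0.43 gave 0.389 against 0.370, a ratio of 1.05.

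**7. What this means.** A ratio of 1.03 equals 1.03² = 1.06, about 6% more patients; 1.042 equals about 9%. For a true interaction ratio of 0.5, power is Φ(0.693/0.431 − 1.96) = 36% with hydroxyurea and Φ(0.693/0.444 − 1.96) = 34.5% without.

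The last column of step 6 shows the chance-imbalance effect. In a single trial the two models' interaction ratios typically differ by a factor of exp(0.11) = 1.12 to exp(0.17) = 1.19, although their averages agree.

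**The case against.** The strongest reply is that little depends on these models. They are labelled exploratory, cannot change the primary analysis, and have low interaction power either way. That stands, and it limits the weight of the point.

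Four stronger readings are tempting, and the documents do not support them:

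- *All subgroup models drop the randomisation stratum.* The hydroxyurea model keeps hydroxyurea. The stratum is hydroxyurea by country, and the primary model does not contain country either. Stratifying by country also largely protects the region subgroup from imbalance.
- *The subgroup results are biased, or not comparable with the primary result.* Steps 4 to 6 show the same treatment and interaction ratios on average. The models are not aligned, but they target the same ratio when hydroxyurea does not modify the effect.
- *Hydroxyurea contaminates the subgroup terms.* At 60% versus 40% use and a rate ratio of 0.43, the subgroup main effect does shift to (0.4 + 0.6 × 0.43)/(0.6 + 0.4 × 0.43) = 0.85. That is the difference in background VOC rate between subgroups. The SAP reports the interaction p-value, which is unaffected on average.
- *The omission costs about 10% of the sample.* This needs a hydroxyurea rate ratio near 0.43, which the documents do not give.

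It could also be argued that SAP 4.1.1 already covers the matter. It says which hydroxyurea value to use (IxRS rather than the eCRF), not that every model must include it. For the subgroup Wilcoxon tests the absence of stratification is stated expressly. It is therefore a choice rather than an oversight, although no reason is given.

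**Conclusion.** The omission is real in six exploratory models and is at odds with the primary model and sensitivity analysis 5. Its consequence is small: no average bias in the treatment or interaction rate ratios; a model-based interaction SE larger by about 0 to 3% for assumed hydroxyurea rate ratios of 1.0 to 0.5, and by about 4 to 5% at 0.43; and less protection against chance hydroxyurea imbalance within subgroups that were not used in randomisation.

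These sizes rest on assumed prevalence and effect, a 50/50 subgroup split, a common treatment effect across hydroxyurea levels, and the planned follow-up. The early termination described in SAP 3.1.4.1 was not modelled. If hydroxyurea modifies the ticagrelor effect, a main effect alone would not separate that from, say, a region effect. The textual finding is certain; its importance is that of a cheap improvement.

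**What to change.** In SAP 4.2.6.4, add IxRS baseline hydroxyurea (Yes/No) as a main effect to the models for age, prior VOC events, genotype, region, gender and race. Leave the hydroxyurea subgroup model as it is. In SAP 4.2.6.2, stratify the matching subgroup Wilcoxon tests by hydroxyurea where stratum sizes allow, except within the hydroxyurea subgroups, where it would do nothing. If the unadjusted form is intended, say why.

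The cost is one model term using data already collected. In small subgroups, such as some race or genotype levels, it may add convergence problems or sparse strata. SAP 4.2.6.4 already falls back to descriptive statistics when a model does not converge, and the same fallback can serve here.
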